5.5 Withdrawal of Subjects and Discontinuation of Study

AbbVie may terminate this study prematurely, either in its entirety or at any site. The study may be discontinued or terminated in case of an unacceptable risk, any relevant toxicity, or a negative change in the risk/benefit assessment. This might include the occurrence of AEs with a character, severity or frequency that is new in comparison to the existing risk profile. In addition, data deriving from other clinical trials or toxicological studies which negatively influence the risk/benefit assessment might cause discontinuation or termination of the study. The investigator may also stop the study at his/her site if he/she has safety concerns. If AbbVie terminates the study for safety reasons, AbbVie will promptly notify the investigator. Advance notice is not required by either party if the study is stopped due to safety concerns.

Subjects can request to be discontinued from participating in the study at any time for any reason. The investigator may discontinue any subject's participation at any time for any reason.

Subjects must have study drug discontinued immediately if any of the following occur:

- The subject requests withdrawal from study drug or the study.
- The investigator believes it is in the best interest of the subject.
- Abnormal laboratory results or AEs that either meet the criteria for discontinuation of study drug as stated in Section 6.2, or rule out safe continuation of the study drug.
- Serious infection (e.g., sepsis) which cannot be adequately controlled by anti-infective treatment or would put the subject at risk with continuation of the study drug.

- Confirmed diagnosis of deep vein thrombosis (DVT), pulmonary embolus or non-cardiac, non-neurologic arterial thrombosis.
- Subject is non-compliant with TB prophylaxis (if applicable) or develops active TB at any time during the study.
- Subject develops any malignancy, except for developing a localized NMSC or a carcinoma in-situ of the cervix if this can be successfully treated at its localization.
- Subject develops a gastrointestinal (GI) perforation (other than due to appendicitis or mechanical injury).
- The subject experiences a serious hypersensitivity reaction without an alternative etiology.
- The subject experiences an anaphylactic reaction or other severe systemic reaction that is related to study drug.
- The subject becomes pregnant while on study drug.

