5.6 Follow-Up After Subject Discontinuation of Study Drug or from Study

Discontinuation of Study Drug

Subjects who prematurely discontinue study drug treatment will be discontinued from study participation entirely.

Following discontinuation of study drug, the subject should be treated in accordance with the investigator's best clinical judgment based on available approved treatment options.

If a subject prematurely discontinues study drug, the procedures outlined for the Premature Discontinuation visit (PD Visit) should be completed as soon as possible, preferably within 2 weeks, and preferably prior to initiation of another therapy. In addition, an End of Treatment Follow-up Visit after the last dose of study drug is required to ensure all treatment-emergent AEs/SAEs have been resolved. The 30-day or 12-week follow-up phone call (for subjects on upadacitinib or dupilumab, respectively) following the last dose of study drug will not be required for any subject who initiates commercially available upadacitinib or dupilumab upon the study Completion Visit or Premature Discontinuation visit. The End of Treatment Follow-up Visit is defined as:

- For subjects on upadacitinib, a 30-day follow-up visit (or phone call if a visit is not possible) after the last study drug dose will be completed to determine the status of any new or ongoing AEs/SAEs and concomitant medications.
- For subjects receiving dupilumab, a 12-week follow-up visit (or phone call if a visit is not possible) after the last study drug injection will be completed to determine the status of any new or ongoing AEs/SAEs and concomitant medications.

For subjects who prematurely discontinued study participation, this visit may be a telephone call if a site visit is not possible.

Premature Discontinuation of Study (Withdrawal of Informed Consent)

If a subject prematurely discontinues study participation (withdrawal of informed consent), the procedures outlined for the Premature Discontinuation visit (PD Visit) should be completed as soon as possible, preferably within 2 weeks, and preferably prior to initiation of another therapy. In addition, if subject is willing, a 30-day or 12 week follow-up phone call or visit after the last dose of study drug (for upadacitinib and dupilumab, respectively) may be completed to ensure all treatment-emergent AEs/SAEs have been resolved.

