6.2 Toxicity Management

The toxicity management of the AEs including AESIs consists of safety monitoring (review of AEs on an ongoing basis), and, if applicable, interruption of study drug dosing with appropriate clinical management and/or discontinuation of the subjects from study drug. The management of specific AEs and laboratory parameters is described below.

Serious Infections: Study drug should be interrupted if a subject develops a serious infection. A subject who develops a new infection during treatment with study drug should undergo prompt diagnostic testing appropriate for an immunocompromised subject. Study drug may be restarted once the serious infection has been successfully treated. Subjects who develop active TB must be permanently discontinued from study drug.

Herpes zoster: If a subject develops herpes zoster, consider temporarily interrupting study drug until the episode resolves.

Gastrointestinal Perforation: If a diagnosis of GI perforation is confirmed (other than due to appendicitis or mechanical injury), the subject must be permanently discontinued from study drug.

Major cardiovascular event: For subjects who develop a major cardiovascular event (MACE: acute myocardial infarction, stroke) while on study drug, the investigator should evaluate the benefit/risk of continuation, and discuss with the TA MD whether it is appropriate to continue study drug.

Malignancy: Subjects who develop malignancy other than NMSC or carcinoma in situ of the cervix must be permanently discontinued from study drug. Information including histopathological results should be queried for confirmation of the diagnosis. Periodic skin examination is recommended for subjects who are at increased risk for skin cancer.

Subjects who develop malignancies should be referred to appropriate specialists and managed as per standard of care.

Muscle-related symptoms: If a subject experiences symptoms suggestive of myositis or rhabdomyolysis, consider checking CPK and aldolase with clinical management and/or study drug interruption as deemed appropriate by the investigator.

Thrombosis Events: Subjects who develop symptoms of thrombosis should be promptly evaluated and treated appropriately. If the diagnosis of deep vein thrombosis, pulmonary embolus or non-cardiac, non-neurologic arterial thrombosis is confirmed, the subject must be discontinued from study drug.

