Management of Select Laboratory Abnormalities: For any given laboratory abnormality, the investigator should assess the subject, apply the standard of care for medical evaluation and treatment following any local guidelines. Specific toxicity management guidelines for abnormal laboratory values are described in [Table 3](#) and may require a supplemental eCRF to be completed. For subjects with ongoing local laboratory abnormalities which may require data entry into an eCRF, an additional local lab eCRF related to subsequent laboratory abnormalities is only required if the subject has relevant changes in history (e.g., new onset signs or symptoms) or laboratory values which have returned to normal reference range or its Baseline value followed by subsequent laboratory abnormalities meeting toxicity guidelines (considered a new event). All abnormal laboratory tests that are considered clinically significant by the investigator will be followed to a satisfactory resolution. If a repeat test is required per [Table 3](#), the repeat testing is to occur as soon as possible.

Table 3. Specific Toxicity Management Guidelines for Abnormal Laboratory Values

Laboratory Parameter	Toxicity Management Guideline
Hemoglobin	
If hemoglobin < 8 g/dL interrupt study drug dosing and confirm by repeat testing with a new sample. If confirmed, continue to withhold study drug until hemoglobin value returns to ≥ 8 g/dL.
 
OR
 
If hemoglobin decreases ≥ 3.0 g/dL from Baseline without an alternative etiology, interrupt study drug dosing and confirm by repeat testing with new sample.
 
 If hemoglobin decreases ≥ 3.0 g/dL from Baseline and an alternative etiology is known or the hemoglobin value remains in the normal reference range, the subject may remain on study drug at the investigator's discretion. If confirmed, continue to withhold study drug until hemoglobin value returns to within 3.0 g/dL from Baseline.
Absolute neutrophil count (ANC)	
If confirmed < 1000/μL by repeat testing with new sample, interrupt study drug dosing until ANC value returns to ≥ 1000/μL.
 
For confirmed < 500/μL, if value returns to ≥ 1000/μL, restarting study drug is allowed if there is an alternative etiology identified; documentation should include reason that rechallenge is expected to be safe for the subject. Study drug should be discontinued if no alternative etiology can be found.

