AST or ALT	
Interrupt study drug if any of the following scenarios are confirmed by repeat testing of AST/ALT:
 
 • ALT or AST > 3 × ULN and either a total bilirubin > 2 × ULN or an international normalized ratio (INR) > 1.5: • A separate blood sample for INR testing will be needed to measure INR at the time of repeat testing for ALT or AST. A repeat test of INR is not needed for determination if above toxicity management criteria are met. • If a creatine phosphokinase (CPK) value is not available, a CPK should be drawn to exclude AST/ALT elevations related to muscle injury • ALT or AST > 3 × ULN along with new appearance of fatigue, nausea, vomiting, right upper quadrant pain or tenderness, fever, rash, and/or new-onset eosinophilia. • ALT or AST > 5 × ULN for more than 2 weeks. 
If ALT or AST > 8 × ULN, interrupt study drug immediately, repeat testing with a new sample, and if repeat test confirms result contact the TA MD
 
Subjects with HBc Ab+ (irrespective of HBs Ab status) and negative HBV DNA PCR testing at Screening who develop the following laboratory findings should have HBV DNA PCR testing performed within 1 week (based on initial elevated value):
 
 • ALT > 5 × ULN OR • ALT or AST > 3 × ULN if an alternative cause is not readily identified. 
A separate blood sample for HBV DNA PCR testing will be needed at the time of repeat testing for ALT or AST.
 
A positive result for HBV DNA PCR testing will require immediate interruption of study drug (unless not acceptable by local practices). Within one week of the first episode of a positive HBV DNA PCR test, a hepatologist consultation should occur for recommendation regarding subsequent treatment.
 
Subjects who meet any of the above criteria should be evaluated for an alternative etiology of the ALT or AST elevation and managed as medically appropriate. If applicable, the alternative etiology should be documented in the eCRF. If ALT or AST values return to the normal reference range or its Baseline value, study drug may be restarted. If restarting study drug, documentation should include reason that rechallenge is expected to be safe. If after clinically appropriate evaluation, no alternative etiology for ALT or AST elevation is found or the ALT or AST elevation has not resolved or is not trending down toward normal, the subject should be discontinued from study drug.
 
For any confirmed ALT or AST elevations > 3 ULN, complete the appropriate supplemental hepatic eCRF(s).

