
Laboratory Parameter	Toxicity Management Guideline
Serum Creatinine	
If serum creatinine is $> 1.5 \times$ the Baseline value and $> \text{ULN}$, repeat the test for serum creatinine (with subject in an euvoletic state) to confirm the results. If the results of the repeat testing still meet this criterion, interrupt study drug and re-start study drug once serum creatinine returns to $\leq 1.5 \times$ Baseline value.
 
For the above serum creatinine elevation scenario, complete the appropriate supplemental renal eCRF(s).

Creatine Phosphokinase	
If a subject experiences any symptoms suggestive of myositis or rhabdomyolysis, blood for measuring CPK and aldolase levels should be drawn with clinical management as deemed appropriate by the investigator.
 
If confirmed CPK value $\geq 4 \times \text{ULN}$ and there are no symptoms suggestive of myositis or rhabdomyolysis, the subject may continue study drug at the investigator's discretion after evaluation.
 
If CPK value $\geq 4 \times \text{ULN}$ accompanied by symptoms suggestive of myositis or rhabdomyolysis, interrupt study drug and contact AbbVie TA MD.
 
For above CPK elevation scenarios, complete supplemental CPK eCRF.

Elective and Emergency Surgeries

For elective and emergency surgeries the following rules will apply:

- If the subject must undergo emergency surgery, the study drug should be interrupted at the time of the surgery. After emergency surgery, allow reintroduction of study drug once the physician has examined the surgical site and determined that it has healed and there is no sign of infection.
- Elective surgery, and interruption of study drug for such a surgery before the primary endpoint visit has been completed must be discussed with the TA MD and only performed with TA MD approval. If the subject undergoes elective surgery, the study drug should be interrupted at least 1 week prior to the planned surgery. Allow reintroduction of study drug once the physician has examined the surgical site and determined that it has healed and there is no sign of infection.

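### Protocol Table 3 gives two outcomes for an ALT/AST elevation that resolves without an identified cause: restart permitted, and discontinuation

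*Protocol*

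**What the plan says.** **ALT/AST.** Once one of the Table 3 liver criteria is met, the subject is evaluated for another cause. The AST or ALT cell then gives two instructions.

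- Restart: "If ALT or AST values return to the normal reference range or its Baseline value, study drug may be restarted". The next sentence asks for a documented reason why rechallenge is expected to be safe. Neither sentence refers to whether a cause was found.
- Stop: after evaluation, if "no alternative etiology for ALT or AST elevation is found or the ALT or AST elevation has not resolved", or if it is not falling toward normal, "the subject should be discontinued from study drug".

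**Force of the stop rule.** Protocol Section 5.5 lists events that oblige the site to stop study drug at once. One is "Abnormal laboratory results or AEs that either meet the criteria for discontinuation of study drug as stated in Section 6.2". Under Protocol Section 5.6, "Subjects who prematurely discontinue study drug treatment will be discontinued from study participation entirely".

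**Muscle symptoms.** The Section 6.2 paragraph on symptoms suggesting myositis or rhabdomyolysis tells the site to "consider checking CPK and aldolase with clinical management and/or study drug interruption as deemed appropriate by the investigator". For the same symptoms, the Creatine Phosphokinase row of Table 3 says that CPK and aldolase should be drawn. For a CPK of at least 4 × ULN it adds: "accompanied by symptoms suggestive of myositis or rhabdomyolysis, interrupt study drug and contact AbbVie TA MD".

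**The concern.** An unexplained liver enzyme elevation is a case where a stopping rule most needs to be clear. Here one site can point to the restart sentence and another to the stop sentence in the same table cell.

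The setting makes this matter more. Hepatic disorder is an adverse event of special interest (Protocol 6.1). Site staff other than the efficacy assessor know the treatment arm (Protocol 4.1 and 5.8). There is no independent data monitoring committee (Protocol 5.10).

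Two reported counts depend on the reading. SAP 10.2 summarises adverse events leading to discontinuation of study drug. SAP 7.3 counts subjects who met withdrawal criteria but were not withdrawn, so a restart made under one sentence could be logged as a deviation under the other.

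There is also a route to the primary endpoint. Stopping drug ends participation, and SAP 9.2 scores a visit missing through early withdrawal as non-response by default.

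**Working it through.** **1. Applying both sentences to each possible state after evaluation**

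| State | Restart sentence | Stop sentence | Result |
|---|---|---|---|
| Resolved, cause found | met | not met | one outcome |
| Resolved, no cause found | met | met (no cause) | **two outcomes** |
| Falling, not yet normal, cause found | not met | met if each limb stands alone; not met if the last two limbs are read together | **unclear** |
| Falling, not yet normal, no cause found | not met | met (no cause) | one outcome |
| Not falling, not normal | not met | met | one outcome |

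The second row is the conflict. The third is an ambiguity. If lack of resolution is enough by itself, the limb about not falling toward normal adds almost nothing, because an elevation that is not falling and not normal is already unresolved. That suggests another reading was intended, but the text does not settle it.

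**2. Comparison within the table**

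For a confirmed neutrophil count below 500/μL that recovers to at least 1000/μL, the ANC row says "restarting study drug is allowed if there is an alternative etiology identified", and otherwise calls for discontinuation. So the link between cause and restart can be stated explicitly. The same row sets no such condition for confirmed counts below 1000/μL that do not fall below 500/μL. It shows only that the link can be written. It is not a template for the liver rule.

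**3. Muscle symptoms**

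On testing, the paragraph says to consider it and the table says it should be done. On interruption, the paragraph leaves it to the investigator and the table directs it once CPK reaches 4 × ULN with symptoms. This concerns testing and interruption, not discontinuation.

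**4. Size of the effect on the primary endpoint**

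Inputs from Protocol 7.9: 880 subjects at 1:1, so 440 per arm; 12% response on dupilumab; a difference of 17 points, so 29% on upadacitinib; two-sided α = 0.05.

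The plan's own figure comes first, with pooled variance under the null:

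- Pooled rate = (0.12 + 0.29)/2 = 0.205
- SE under the null = √(2 × 0.205 × 0.795/440) = 0.0272
- SE under the alternative = √((0.12 × 0.88 + 0.29 × 0.71)/440) = 0.0266
- z = (0.17 − 1.96 × 0.0272)/0.0266 ≈ 4.38, so power ≈ 0.99999

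This agrees with the stated power of more than 90%.

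The documents give no frequency for resolved, unexplained elevations. Assume 1–2% of an arm, which is 4.4–8.8 of 440 subjects.

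- One would-be responder lost moves an arm by 1/440 = 0.23 points.
- Upadacitinib, at 29%: 0.29 × 1% to 0.29 × 2% = 0.29–0.58 points (about 1.3–2.6 responders).
- Dupilumab, at 12%: 0.12 × 1% to 0.12 × 2% = 0.12–0.24 points (about 0.5–1.1 responders).

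Stress test, losing would-be responders from the upadacitinib arm only:

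| Responders lost | Difference (points) | Power |
|---|---|---|
| 0 | 17.0 | 0.99999 |
| 5 | 15.9 | 0.99997 |
| 10 | 14.7 | 0.9999 |
| 20 | 12.5 | 0.998 |

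At a 29% response rate, losing 20 responders would need about 20/0.29 ≈ 69 affected subjects, or 69/440 ≈ 16% of the arm.

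**The case against.** The best defence is that the two sentences form a sequence. Restart is only permitted, and it needs a documented justification. The stop sentence comes last, after evaluation, and Section 5.5 turns the Section 6.2 discontinuation criteria into an obligation. An obligation normally limits a permission. This has force. A reader might infer that sites can do opposite things and both comply fully; the documents do not support that, because a site that restarts is exposed under Section 5.5. But neither Table 3 nor Section 5.5 states the precedence, and Table 3 is framed as guidelines and says should, so the gap remains.

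On the falling elevation, the last two limbs can be read together as neither resolved nor improving. That reading is available, which is why the point is ambiguity and not contradiction.

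On muscle symptoms, the triggers differ: symptoms alone in the paragraph, symptoms plus raised CPK for interruption in the table. Table 3 is also described as the specific guidance. The mismatch on whether to draw blood survives, and so does the one on whether interruption is discretionary once CPK is high, but both are secondary.

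A reader might also infer that a stopped subject automatically becomes a non-responder. That goes too far. Discontinuation is handled by treatment policy (Protocol 7.3, SAP 8.0). SAP 9.2 and Appendix H send data judged missing at random to multiple imputation. EASI and WP-NRS are scheduled at the premature discontinuation visit and could supply a value within the Week 16 window. In addition, Protocol Appendix D schedules central chemistry only at Week 4 between Baseline and Week 16, which limits how many elevations routine testing can detect in time to remove the Week 16 assessment.

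**Conclusion.** The inconsistency is real and narrow. A resolved ALT/AST elevation with no identified cause meets both a sentence permitting restart and a sentence calling for discontinuation, and the second becomes mandatory through Section 5.5 without the table saying that it prevails. Whether a falling but not yet normal elevation is a reason to stop is unclear. The muscle-symptom paragraph and the CPK row also need aligning.

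The consequence is uneven application of a safety stopping rule, and discontinuation and deviation counts that depend on how each site reads it.

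The effect on the primary endpoint is small: about 0.3–0.6 points in the upadacitinib arm. This rests on an assumed 1–2% of subjects affected, on those subjects responding at the planned 29%, and on every one of them being scored as a non-responder, so it leans high. A reader might infer a shift of 1–2 points, but that would require every affected subject to have been a responder. The primary conclusion is not threatened: power stays at about 99.8% even with 20 upadacitinib responders lost.

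**What to change.** Reconcile the restart and stop sentences in the AST or ALT row of Table 3 with each other and with Section 5.5, so that one outcome is stated for each of:

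- an elevation back to normal or Baseline with no alternative cause found;
- an elevation falling but not yet normal.

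State which text governs where Table 3 and Section 5.5 both apply, so that the deviation category in SAP 7.3 is applied in the same way at all sites. Secondarily, reconcile the muscle-symptom paragraph of Section 6.2 with the Creatine Phosphokinase row on testing and on interruption.

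Which outcome applies in each case is a clinical decision for the sponsor, and this review takes no position on it. The cost is a wording clarification in the protocol and notice to sites. No new procedure, data or analysis is needed.

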7 STATISTICAL METHODS & DETERMINATION OF SAMPLE SIZE

7.1 Statistical and Analytical Plans

The statistical methods provided in this protocol will be focused on primary and ranked secondary endpoints analyses. Complete and specific details of the statistical analysis will be described in the Statistical Analysis Plan (SAP).

The statistical analyses will be performed using SAS (SAS Institute Inc., Cary, North Carolina, USA).

The primary analysis will be conducted after all ongoing subjects have completed the Week 16 visit or permanently discontinued Period 1, and all data pertaining to Period 1 are cleaned. This analysis is the final and only analysis for the primary and ranked secondary endpoints.

